Protocol Title:

Educating Women about Pelvic Floor Disorders during Pregnancy From the 1st to the “4th trimester”

Principal Investigator:

[name] FPMRS, Houston Methodist Hospital, Houston, TX

Co-Investigators:

[name] MD FPMRS, Houston Methodist Hospital, Houston, TX

[name] MD FPMRS, Houston Methodist Hospital, Houston, TX

[name] PhD, University of Houston, Houston, TX

SPONSOR / FUNDING AGENCY

None

VERSION NUMBER/DATE

Version 8 10/8/20

REVISION HISTORY

Revision #	Version Date	Summary of Changes	Consent Change (Yes/No)
1	7/1/20	Addition of virtual version of workshops	Yes
2	10/8/20	Addition of postpartum phone follow up	No

1. Study Summary

Pelvic floor disorders (PFDs) are common and significantly affect the quality of life of many women as they age. Pregnancy has been identified as a major risk factor for developing PFDs later in life. Educating women about PFDs is essential to ensuring that they present to care in a timely manner. No study has investigated different education tools during pregnancy. The proposed study is a randomized controlled trial in pregnant patients comparing two educational tools: written materials about PFDs versus an educational workshops led by pelvic floor physical therapists (PFPTs). Pregnant patients will be recruited in the first and second trimester and randomized at that time. Knowledge will be assessed at baseline and again 6 weeks postpartum using the validated Prolapse and Incontinence Knowledge Questionnaire. Secondary outcomes will be evaluating referral patterns to urogynecology and to PFPTs from general OBGYNs and assessing any pelvic floor symptoms with the pelvic floor disability index (PFDI-20) at baseline and at 6 weeks postpartum.

2. Purpose of the Study / Objectives

Hypothesis: Patients attending an educational workshop from pelvic floor physical therapist (PFPT) on pelvic floor anatomy, physiology, and disorders will have improved knowledge of pelvic floor disorders (PFDs) as measured by the Prolapse and Incontinence Knowledge Questionnaire (PIKQ) than those in the written education group.

Primary aim:

To determine the change in knowledge regarding PFDs as measured by the PIKQ in pregnant patients attending education compared to written education alone.

Secondary aims:

To determine whether pregnant patients receiving written education or attending an educational workshop on PFDs increases referral rates to either PFPT or urogynecology.

To evaluate the incidence of PFD symptoms among pregnant patients throughout their pregnancy, including the "4th trimester" postpartum period (or the 12 weeks following delivery) using validated Pelvic Floor Disability Index (PFDI-20).

3. Background

Pelvic floor disorders (PFDs) in females can occur in many phases of life some of which are better understood than others. Pregnancy and delivery have been well established as major risk factors for developing PFDs.¹ The American College of Obstetrics and Gynecologists (ACOG) has made a renewed effort to bring attention to many health issues women experience due to pregnancy and the postpartum period by focusing on the "fourth trimester", referring to the 12 weeks following delivery. In May of 2018, the ACOG committee opinion focused on redefining the postpartum visit. One of the areas described in the physical recovery is assessment of the perineum and the presence of PFDs such as fecal or urinary incontinence.² There are a wide variety of physical and mental health topics that need to be discussed in each perinatal visit and pelvic floor issues may not be addressed.

Prior studies have evaluated the information that patients receive during pregnancy and the most neglected area was educating patients on PFDs. Obstetricians cite their concern about patients developing PFDs in the future as a factor that they consider in their obstetric management during delivery.³ Patients are not well informed on their risk of developing PFDs and would be more equipped to participate in their care during pregnancy, during their delivery, and after pregnancy if they were better informed. Furthermore, many women have misconceptions about PFDs and are unaware of what their risks are and that there are prevention strategies and treatment options available to them.⁴ When patients have been asked about their perception of PFDs in one-on-one interviews, the findings suggested that younger women were less educated about PFDs while older women were more embarrassed to discuss these issues with others.⁵ The goal of this study is to investigate the best method for educating patients in the antepartum period and following them into the postpartum period to assess their retention of knowledge from the education they received.

Previous studies have examined this issue by various means of educating patients in different stages of the postpartum period. One such study examined immediate postpartum education on

perineal lacerations using a 3-D anatomical model and the effect it had on changing patient anxiety and knowledge. Patient anxiety decreased and patient knowledge increased after education using this model.⁶ Gagnon, et al. approached this issue by offering postpartum patients direct interaction with pelvic floor physical therapists in a group and one-on-one setting.⁷ Both of these studies showed that educating women about PFDs can lead to an improved understanding of their symptoms. In Gagnon's study, the patients that were educated in a group workshop setting led by PFPTs showed similar satisfaction and improvement in PFDI-20 scores to those patients that met with PFPTs in one-on-one sessions. This study would seek to continue the efforts of prior studies by further comparing patient education tools. The innovation of this study lies in the patient population and intervention comparison. The interventions that we will compare are written educational material versus an educational workshop setting with PFPTs. By intervening earlier in pregnancy, we hope to capture a unique patient population and intervene earlier to try to improve their knowledge of PFDs throughout pregnancy, the postpartum period, and beyond into the remainder of their life. There are no prior studies that have taken this approach of educating patients during pregnancy using the PIKQ as a validated measure of knowledge.

4. Study Design

The study design is a randomized controlled trial. There will be two study groups with 60 participants in each (total study population of 120 participants.) The participants will be randomized into: Group 1- written education group and Group 2-PFPT workshop group. Patients will be recruited from the obstetric population at our institution in the first and second trimester during their scheduled prenatal visit.

Statistical Analysis:

Patients' baseline characteristics will be summarized according to the two groups. All data will be presented as mean \pm SD or median (interquartile range) for continuous variables, and number (percentage) for categorical variables. Chi-squared or Fisher's exact test (categorical variables) and Student's t-test or Mann-Whitney test (continuous variables) will be used to compare patients between PFPT and written education group at baseline. Paired t-test or Wilcoxon signed-rank test will be used to compare questionnaire scores between baseline and the follow-ups within each group. Student's t-test or Mann-Whitney test will be used to compare the paired difference between the two groups. The Shapiro-Wilk test will be used to check the normality. Pearson's correlation coefficient or Spearman's rank correlation coefficient will be used to analyze the relationships among variables. All analyses will be performed with STATA version 16 (StataCorp. 2019. Stata Statistical Software: Release 16. College Station, TX: StataCorp LLC). Statistical significance will be defined as two-tailed $p < 0.05$ for all tests.

Sample Size Calculation:

Our primary objective of the proposed study is to evaluate the hypothesis that patients attending an educational workshop from PFPTs will have improved knowledge of pelvic floor disorders (PFDs) as measured by the Prolapse and Incontinence Knowledge Questionnaire (PIKQ) as compared to patients in the written education group. We will use the 24-point PIKQ questionnaire composite score as our primary endpoint. Based on the PIKQ validation study, a composite score of 0.45 (45%) is expected in women of this age at baseline.⁸ Assuming in our study population at baseline a score of 0.45, we would expect an increase in the composite

score to 0.8 in the PFPT group and an increase in composite score to 0.54 in the written education group. Therefore, a sample size of 96 patients will be needed to detect the difference with 80% power and a significance level of 0.05 based on the two-sided Z-test with pooled variance. After considering 20% dropout rate from the study, the total sample size will be 120 patients (60 per group). PASS 2015 (PASS 15 Power Analysis and Sample Size Software (2017). NCSS, LLC. Kaysville, Utah, USA, ncss.com/software/pass) was used for sample size calculation.

Study Timeline:

The obstetrics practice that we will be recruiting from has approximately 75 obstetrics patients per month. Assuming approximately 50% recruitment each month, we anticipate being able to complete recruitment in 6 months. We will start educational workshops once 10 patients are enrolled into the educational workshop arm of the study. In order to offer adequate availability to patients, we will plan to offer four workshops per month. As scheduling the workshops may pose a logistical challenge, we will assess patient availability and adjust timing of the workshops to maximize the number of patients at each workshop. We will continue to follow these patients through their pregnancy so the timeline of data collection will continue for approximately 9 months after the recruitment period ends. We estimate that data collection will be completed by August 2021.

2020			
July			
Aug			
Sept			
Oct			
Nov			
Dec			
2021			
Jan			
Feb			
Mar			
Apr			
May			
June			
July			
Aug			

Recruitment period

Educational workshops
four times per month

Data collection period will
continue until 3 months after the
completion of the intervention to
capture both questionnaire and
referral pattern data.

Inclusion criteria:

- Patients in the first or second trimester of pregnancy
- English speaking
- Greater than 18 years old

Exclusion criteria:

- Non-English speaking or unable to provide informed consent

5. Study Intervention

At the first research visit, patients will be consented and randomized. Patients may be approached regarding the study by phone. The research consent form will be sent to them via e-mail for them to review and they will sign the consent at their next in-person visit. They will complete the PIKQ and PFDI-20 questionnaires (Appendix A).^{8,9} After their baseline questionnaires are completed, they will receive written educational materials.

Patients randomized into the written education group will only receive written materials. They will receive these materials at the first study visit and again when leaving the hospital after delivery. The written materials will consist of three one-page handouts with information on pelvic organ prolapse (POP), stress urinary incontinence (SUI), and pelvic floor exercises. These handouts will be created in collaboration with [name] and [name] who have experience in the study of patient's perceptions of PFDs and have collaborated with the American Urogynecology Society to create written educational materials in the past.⁴ We plan to seek feedback from patients regarding their impressions of our newly developed handouts prior to use.

The PFPT workshop group will both receive the written handouts and attend an in-person education workshop that will be led by a PFPT with approximately 5-10 study participants in each workshop. Patients will be allowed to attend the workshop after being randomized during pregnancy or during the postpartum period to maximize participation. The session will last approximately 1 hour and will review similar information to the content of the handouts. It will focus on educating the patients about pelvic floor anatomy, etiology of PFDs, prevention strategies, and informing them about urogynecologists and PFPTs. The educational workshops will be offered in either in person or virtual format to accommodate group gathering restrictions of COVID-19. The web-based meeting will be password protected and participants will have the option to share their video and do not have to provide their name as the participant if they do not want to. They have the option to verbally participate but this is not required.

Patients will be reassessed and complete the PIKQ and PFDI-20 questionnaires at their 6-week postpartum visit. We will also record delivery type. If patients do not attend their postpartum visit, they will be reached by phone or e-mail to complete the postpartum assessment. Referral patterns to PFPT and urogynecology will be assessed using electronic medical records during the study period and up to 3 months postpartum.

Patients from the workshop group will receive a follow up phone call to perform a brief phone survey on their perceptions of the two forms of educational materials: written versus workshop format. No medical information will be discussed in this phone call. Please see interview guide attached in appendix ***.

6. Drugs, Biologics, Devices

No drugs, biologics, or devices will be used for this study.

7. Collaborative / Multi-site Research

This study will take place at one site within the Methodist system.

8. Data Privacy / Confidentiality

Houston Methodist policies for Protected Health Information (PHI) will be followed in access patient charts. PHI will be used to identify patients that are eligible for the study by reviewing clinical schedules. Patients will be assigned a subject ID number that is deidentified. There will be a master data sheet that will have patient MRNs associated with their subject ID number that is separate from the RedCap database. This data sheet will be stored on an encrypted password protected USB drive. No PHI will be disclosed. The data will be maintained for 6 years after the completion of the study and then destroyed.

The web based virtual workshop will not include the patient's personal information, including their name, unless they want to provide their name. They have the option to share their video or participate verbally in the workshop but it is not required. All participants will be muted and their video off on entry to the virtual meeting and they can choose to disable these features if desired. The virtual workshop meeting room will be password protected. This password will be provided to the participants via e-mail the day of the workshop. There will be a phone number to a study team member provided to them to call for any technical support if needed. None of the sessions will be recorded.

Identifier (or parts of)	Recorded	Disclosed	Comment
All elements of dates (except year) for dates directly related to an individual, including birth date, admission date, discharge date, date of death; and all ages over 89 and elements of dates (including year) indicative of such age	X		
Medical record numbers	X		
Phone number			Used for recruiting patients after virtual visits with their doctor.
Email address			Used to send questionnaires and consent forms if recruited virtually. Used to send password for virtual workshop.

9. Data and Specimen Banking

Patient demographic data will be collected from the medical record and the PIKQ survey, including age, race, obstetrics history, marital status, household income, and education level. Delivery type will also be recorded at the 6 weeks postpartum visit. The patients will be asked to give responses to the PIKQ and PFDI-20 surveys. Data collected in the study will include referral patterns within the OBGYN group at Methodist to the urogynecology group and pelvic floor physical therapy group. The referral information will be collected for the 6 months

preceding the study and compared to the data collected during the study period. This data will be recorded on recruitment paperwork with a de-identified subject ID and recorded into a RedCap database.

10. Study Population

We will recruit female patients in the first or second trimester of pregnancy who are 18 years of age or older.

11. Screening and Recruitment^{SR}

Patients will be identified by reviewing the clinical schedule of the general obstetrics providers at Houston Methodist Hospital. The patients will be approached either in the waiting room prior to their appointment or while they are awaiting their physician visit in the clinic room. Patients may also be approached by phone after their visit with a physician if they are attending virtual visits. Recruitment flyers will be posted around the clinical area and waiting room of the Smith 2221 OBGYN clinical area.

12. Withdrawal of Subjects

Subjects may withdraw from the study at any time with no change to their routine obstetric care. Patients who experience a miscarriage or intrauterine fetal demise prior to viability will be withdrawn from participation.

13. Provisions to Protect the Privacy Interests of Subjects

Subjects will be required to provide minimal demographic information at their recruiting visit and this will not need to be repeated at any point. Their primary interaction with the research study team will be at recruitment, at the PFPT group workshop, and at their postpartum visit for the follow up questionnaire administration. The educational workshop will include females only and female PFPTs in small groups of 5-10 subjects. We plan to offer the workshops in either an in-person or virtual format to accommodate for current group gathering constraints due to COVID-19.

14. Risks to Subjects

There are minimal risks associated with this study. The cost of parking in the medical center may pose a burden to some subjects and so we plan to compensate the cost of parking to try to offset this. Otherwise, there is no physical, social, legal, or psychological risk to the subjects.

15. Potential Benefits

Regardless of the group to which the subjects are randomized, they will be given education on PFDs that they would not typically receive in their routine obstetric care. This may provide the opportunity to make subjects aware of treatment options for PFDs that they were not aware of and provide them an opportunity to improve their quality of life.

A potential challenge would be ensuring that patients receive their follow up assessment as patients may not show up for their postpartum visit. A strategy to improve follow up would be to consent patients to the option of receiving and completing the PIKQ and PFDI-20 by e-mail if they do not attend their postpartum visit. Another potential challenge may be ensuring that patients attend their assigned group workshop. A strategy to improve attendance and

enrollment would be to compensate patients. We plan to compensate their parking on the dates that they attend the group workshop.

16. Financial and Economic Issues

The only cost to the study subjects will be the cost of parking to attend the group workshop. The remainder of the study visits will occur at the same time as routine care visits. We will plan to compensate the cost of parking at the time of their group workshop with an estimated cost of \$960 (\$16 per participant).

17. Data Safety Plan

Please see above description of Data and Specimen Banking.

18. Informed Consent Documentation and Process

Informed consent will be obtained prior to any of the study procedures with the attached informed consent template. Consent will be obtained from a member of the research team. The consent document may be e-mailed to participants after being recruited by phone for their review. They will then sign the consent form at their next in-person physician visit.

19. Waiver of Informed Consent and /or Authorization

A screening waiver will be requested preparatory for research (waiver requested for feasibility, recruiting, access to charts, pre-screening). We are not requesting a waiver of informed consent.

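### The primary PIKQ comparison should be one pre-specified baseline-adjusted mean difference; the planned change-score test is valid, but usually less precise, and leaves the effect measure open.

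*Combined protocol and SAP*

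**What the plan says.** The primary aim (Section 2) is "To determine the change in knowledge regarding PFDs as measured by the PIKQ", workshop against written education. The endpoint is the 24-point PIKQ composite, measured at baseline and 6 weeks postpartum. Under Statistical Analysis in Section 4 the only between-arm analysis of that change is "Student's t-test or Mann-Whitney test will be used to compare the paired difference between the two groups". The next sentence adds "The Shapiro-Wilk test will be used to check the normality", without saying which variable is checked, in which arm, or what follows from the result. The same paragraph sets two-tailed p < 0.05 for every test. It names no baseline-adjusted model, and no effect estimate or confidence interval for the primary comparison.

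Baseline scores precede any teaching: "After their baseline questionnaires are completed, they will receive written educational materials" (Section 5). The sample size text takes 0.45 at baseline in the study population, 0.80 at follow-up in the workshop arm, and "an increase in composite score to 0.54 in the written education group". It arrives at 96 evaluable women, raised to 120 "After considering 20% dropout rate from the study".

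**The concern.** There are two points.

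First, a change score forces the slope of follow-up on baseline to equal 1. Unless that slope really is 1, subtraction uses the baseline inefficiently, and a regression on baseline gives a more precise estimate of the same quantity. The covariate is already being collected.

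Second, the t-test and the Mann-Whitney test answer different questions: a difference in mean change, and a shift in ranks. If a normality check picks between them, the data decide which effect measure is reported. If it does not, the choice is simply unspecified.

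At stake are the width of the confidence interval, power if the true difference is smaller than planned, and whether the reported effect measure is known in advance.

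**Working it through.** **Inputs from the documents.** Follow-up means 0.80 and 0.54, baseline 0.45 in both arms, 48 evaluable per arm, two-sided 0.05. The planned difference in change is (0.80 − 0.45) − (0.54 − 0.45) = 0.35 − 0.09 = 0.26.

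**Assumed, because the documents give no value.** Correlation ρ between baseline and follow-up, 0.3 to 0.7; ratio k of follow-up SD to baseline SD, 0.7 to 1.3; SD of the change score, 0.20 to 0.30 on the 0–1 scale.

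**The plan's own figure.** A two-proportion calculation with unpooled variance gives (1.960 + 0.842)² × (0.80×0.20 + 0.54×0.46) / 0.26² = 47.4, so 48 per arm and 96 in total; 96/0.80 = 120. The pooled-variance formula that the text names gives 50.1, so 51 per arm and 102. Neither contains an SD for the score, so the sizing does not show how precise the planned t-test will be.

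**Variance of the adjusted estimate relative to the change score.** The ratio is k²(1 − ρ²) / (1 + k² − 2ρk), which reduces to (1 + ρ)/2 when k = 1.

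| k | ρ = 0.3 | ρ = 0.5 | ρ = 0.7 |
|---|---|---|---|
| 0.7 | 0.42 | 0.47 | 0.49 |
| 1.0 | 0.65 | 0.75 | 0.85 |
| 1.3 | 0.81 | 0.91 | 0.99 |

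**Confidence interval.** With equal SDs the width is multiplied by √0.65 to √0.85, that is 0.806 to 0.922, or about 19% to 8% narrower. For a change SD of 0.30, the half-width 1.986 × 0.30 × √(2/48) = 0.122 falls to 0.098–0.112. At a ratio of 0.99 it is 0.121, in effect unchanged.

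**Power (noncentral t, 48 per arm).** At 0.26, change-score power is 98.8% at change SD 0.30, 99.9% at 0.25 and above 99.9% at 0.20. At 0.13, half the planned difference and chosen only as an illustration:

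| Change SD | Change score | Adjusted, ratio 0.85 to 0.65 |
|---|---|---|
| 0.20 | 88% | 93–97% |
| 0.25 | 71% | 78–88% |
| 0.30 | 56% | 63–74% |

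**Bounded-score check.** A simulation used 24 binomial items, logit-normal ability with SD 0.6, 1.0 or 1.4, latent correlation 0.5, 0.7 or 0.9, and 4,000 runs per setting. At the planned means the variance ratio was 0.55–0.77, the change SD 0.14–0.29, and both estimators averaged 0.26. Shapiro-Wilk gave p < 0.05 in at least one arm in 13–24% of trials; that is how often Mann-Whitney would be reported if the check selects the test. With no difference between arms, type I error was 4.3–5.4% for the two-stage rule and 4.3–5.7% for the HC3 model.

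**The case against.** The strongest reply is that nothing is broken. The change score matches the wording of the primary aim, the test is valid under randomisation with complete follow-up, power at 0.26 is ample, and the two-stage rule does not inflate type I error. All of that stands, and it is why this is a recommendation and not a correction. The adjusted model does not abandon the aim: regressing follow-up or change on arm and baseline gives the identical arm coefficient.

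A second reply is that the gain depends on unknown inputs. That also stands. If follow-up scores are more variable than baseline scores and strongly correlated with them, the gain nearly vanishes. A change SD of 0.30 lies just above the simulated range of 0.14–0.29, so the last row of the power table is an unfavourable edge and not the expected case.

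Third, the sizing is weak evidence of the intended effect measure. The expected scores suggest a mean difference, but 96 comes from a formula for proportions.

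Some stronger readings are tempting but not supported:

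- A reader might infer that the Shapiro-Wilk check has no threshold. Section 4 sets p < 0.05 for all tests; only the variable, the arm and the consequence are missing.
- A reader might infer that the plan expressly makes Shapiro-Wilk select the test. It does not say so; that is the natural reading, with no other rule given.
- A reader might infer that teaching in groups invalidates the test. Section 5 has workshops "led by a PFPT with approximately 5-10 study participants in each workshop", but the timeline offers four a month. Over 6 months that is 24 sessions, or 48/24 = 2 evaluable women each if all were held. The documents give neither the realised session size nor a within-session correlation. This is a separate question.

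**Conclusion.** The point holds as a free improvement in precision and pre-specification. It does not show that the planned test is biased, that its error rate is wrong, or that the trial is underpowered for 0.26; a reader might infer any of these, and the checks point the other way.

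The expected benefit is an interval about 8–19% narrower under equal SDs and ρ of 0.3 to 0.7, with a possible range from almost nothing to a variance ratio of 0.42. Power benefits only if the true difference falls well short of 0.26. The statement that power is about 99% or more rests on a change SD no larger than 0.30; at 0.45 it would be 80%. Fixing the effect measure is worthwhile whatever the correlation, because it settles beforehand what will be reported.

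**What to change.** In Section 4, name one primary analysis: a linear model of 6-week postpartum PIKQ on assigned arm, with baseline PIKQ as covariate and HC3 robust standard errors. Report the adjusted mean difference with its 95% confidence interval. Keep Mann-Whitney on the change score as a sensitivity analysis, and drop the normality check as a way of choosing the test.

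Section 5 mentions randomisation before the baseline questionnaires, so confirm that baseline PIKQ is completed before the woman learns her allocation. The change score needs this just as much.

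The cost is SAP wording, a few lines of code and one degree of freedom; no extra women, visits or data are needed. The change does not deal with the expected 20% dropout, for which the plan states no missing-data method, or with correlation within workshop sessions. Both need their own decisions.

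### The 96-patient, 80%-power statement does not follow from its stated inputs for the planned test on PIKQ change, because no SD is given

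*Combined protocol and SAP*

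**What the plan says.** Section 2 sets the primary aim: "To determine the change in knowledge regarding PFDs as measured by the PIKQ in pregnant patients attending education compared to written education alone". In section 4, the Sample Size Calculation fixes the outcome: "We will use the 24-point PIKQ questionnaire composite score as our primary endpoint". The Statistical Analysis text gives the between-group comparison of change: "Student's t-test or Mann-Whitney test will be used to compare the paired difference between the two groups", with normality checked by the Shapiro-Wilk test and significance at two-tailed 0.05.

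The sample size rests on expected mean scores. At baseline, "a composite score of 0.45 (45%) is expected in women of this age at baseline". At follow-up the plan expects the composite "score to 0.8 in the PFPT group and an increase in composite score to 0.54 in the written education group". From these it concludes that "a sample size of 96 patients will be needed to detect the difference with 80% power and a significance level of 0.05". The same sentence names the method behind this figure, which it describes as "based on the two-sided Z-test with pooled variance". Allowing for 20% dropout, the total becomes 120, or 60 per group.

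The protocol and SAP give no SD of the PIKQ score or of its change, no correlation between baseline and follow-up, and no standardised effect size.

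**The concern.** A comparison of mean change cannot be sized from means alone; it needs the SD of change, or a score SD together with a baseline to follow-up correlation. A comparison of two proportions, by contrast, can be sized from two numbers between 0 and 1, because the variance follows from the proportions. The paragraph supplies two such numbers and nothing else, although 0.80 and 0.54 are average fractions of a 24-point score and not proportions of women.

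At stake is the only power statement for the primary endpoint. As written, a reader cannot check 96 or 80% against the planned test, and cannot tell how small a difference in PIKQ change the trial could detect. That second point matters for interpreting a null result, because the target difference is large: 0.26 × 24 = 6.24 of 24 points.

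**Working it through.** **Inputs from section 4.** Follow-up means 0.80 (workshop) and 0.54 (written); common baseline 0.45, so changes of 0.35 and 0.09; difference 0.26 on either basis. Two-sided 0.05, 80% power, 1:1 allocation, dropout 20%. The normal quantiles are 1.960 and 0.8416; their sum is 2.8016, and its square 7.849.

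**1. Reproducing 96: two proportions, unpooled variance.**
n per group = 7.849 × (0.80×0.20 + 0.54×0.46) / 0.26² = 7.849 × 0.4084 / 0.0676 = 47.42, so 48 per group and 96 in total. Dropout: 96 / 0.80 = 120, as stated.

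**2. Two proportions, pooled variance (the plan names a pooled-variance Z-test).**
Mean proportion 0.67.
n per group = [1.960 × √(2×0.67×0.33) + 0.8416 × √0.4084]² / 0.0676 = (1.3033 + 0.5378)² / 0.0676 = 50.15, so 51 per group and 102 in total.
Power of this test at 48 per group: Φ[(0.26×√48 − 1.3033) / √0.4084] = Φ(0.779) = 78.2%; exact binomial enumeration gives 79.1%.

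**3. Z-test of means with a common SD.**
n per group = 2 × 7.849 × SD² / 0.0676. At SD 0.45 this is 47.02, which rounds up to 48. The result is 48 only for SDs from 0.450 to 0.455 (10.8 to 10.9 of 24 points), and no such SD is stated.
- As an SD of follow-up scores, this is at the mathematical limit. For a 0-1 score with means 0.80 and 0.54, the pooled SD cannot exceed √[(0.16 + 0.2484)/2] = 0.452, reached only if every woman scores 0 or 24.
- As an SD of change, 0.45 is possible, and the planned t-test would then have 80.0% power. On that reading the 80% is unsupported, not wrong.

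**4. The planned t-test at 48 per group (noncentral t, independent participants).**
The difference detectable with 80% power is 0.578 SD of change. Power for 0.26 therefore reaches 80% when the SD of change is 0.26 / 0.578 = 0.450 (10.8 points) or less. All SDs below are assumptions.

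| Assumed SD of change | Power for 0.26 | Detectable at 80% power (0.578 × SD × 24) |
|---|---|---|
| 0.15 | above 99.9% | 2.1 points |
| 0.25 | 99.9% | 3.5 points |
| 0.30 | 98.8% | 4.2 points |
| 0.40 | 88.3% | 5.5 points |
| 0.45 | 80.0% | 6.2 points |

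**5. How extreme is an SD of change above 0.45?**
With equal score SDs s at both visits and correlation r, SD of change = s × √[2(1 − r)]. At r = 0 it exceeds 0.45 only if s exceeds 0.318; at r = 0.5, only if s exceeds 0.450. Scores spread evenly over 0 to 24 have an SD of √[(25² − 1)/12] / 24 = 0.300. With that spread at both visits and r = 0, the SD of change is 0.425 and power is about 84%.

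**The case against.** The strongest reply is that this is a gap in reporting with no consequence for the design. An SD of change above 0.45 needs scores more dispersed than an even spread over the whole scale, or a negative correlation between visits. For the stated target the trial is therefore adequately sized under any realistic spread. That stands, and it limits the point. A reader might infer from the missing SD, or from the 78-79% figure, that the trial is underpowered. The documents do not support this: the 78-79% belongs to a test of two proportions that the plan does not intend to run on a 24-point score.

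A second reply is that the two-proportion reading is conjecture. The text never calls the scores proportions of women, the named method is pooled while the match is to the unpooled formula, and the software settings are not shown. An SD may also have been taken from the cited validation study. This stands in part. A reader might conclude that the score was certainly treated as binary; that remains an inference. But the main finding does not depend on it. Whatever produced 96, the SD needed to tie it to the planned test is not in the plan.

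A third reply is that 78-79% is close to 80% and 102 is close to 96. That is true, and the size of this gap is not the reason to act.

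**Conclusion.** The point holds as one of traceability. The stated inputs do not lead to 96 patients and 80% power for a t-test or Mann-Whitney test on PIKQ change. They lead to 96 by an unpooled two-proportion formula; the pooled version gives 102, and a Z-test of means gives 96 only with an unstated SD of 0.450-0.455. The dropout step is correct.

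Power for the 0.26 target is at least 80% with a t-test at 48 evaluable women per group, provided that the SD of change is 0.45 or less and participants are independent. It is probably well above that: 88.3%, 98.8% or 99.9% at assumed SDs of 0.40, 0.30 or 0.25. These SDs are illustrations, since the documents give none. Independence is also an assumption to state, because the workshop is "led by a PFPT with approximately 5-10 study participants in each workshop"; whether it holds is a separate question. The paragraph should be corrected, since it is the only power statement for the primary endpoint, but the design is not in doubt on this account.

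**What to change.** Replace the calculation with a two-sample t-test on the change in PIKQ score. State the SD of change, its source and a range of values. If it is derived from a score SD, state the assumed baseline to follow-up correlation as well. Then restate the power or the detectable difference. Possible wording:

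> 48 evaluable women per group give 80% power at two-sided 0.05 to detect 0.58 SD of PIKQ change, i.e. 2.1, 3.5 or 5.5 of 24 items if the SD of change is 0.15, 0.25 or 0.40, assuming independent participants.

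Add that a Mann-Whitney test, if used, would have slightly different power. The proportion-type calculation should not be kept with a corrected power figure, because it does not describe the planned test.

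The cost is one rewritten paragraph. The planned 120, the endpoint and the test do not need to change.
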